Indication- To compare the effects of proparacaine before and after povidone iodine application on patient experience, and to compare bacterial colonies in conjunctival cultures obtained from patients undergoing intravitreal injection to ensure adequate antisepsis.

General approach/Treatment plan (See figure 1)- The study will take place during intravitreal injections. The anticipated study is as follows: After a procedural time out to verify patient, agent, and laterality, proparacaine will be applied to the ocular surface. A conjunctival culture will then be obtained followed by the application of povidone-iodine to the eyelashes and eyelid margins. The eyelids will then be retracted away from the intended injection site for the duration of the procedure. At this point, half of the patients will be randomized to receive 5% povidone-iodine drop to the conjunctival surface followed by conjunctival culture then re-application of 5% povidone-iodine drop to the conjunctival surface. A needle will then be inserted perpendicular to the sclera, 3.5-4.0 mm posterior to the limbus between the vertical and horizontal rectus muscles. The other half of patients will undergo application of another drop of topical anesthetic followed by conjunctival culture. After the culture, this group of patients will have 5% povidone iodine applied to the conjunctival surface. A needle will then be inserted perpendicular to the sclera, 3.5-4.0 mm posterior to the limbus between the vertical and horizontal rectus muscles.

STUDY NAME

Figure 1

** the circles highlight deviations from the typical protocol

Human subjects

Sixty patients (male and female) undergoing intravitreal injection who do not have active eye infections will be enrolled after undergoing informed consent.

Exclusion criteria: 1. Age less than 18. 2. Patients with active eye infections

[figure not shown]
The main risk encountered by human subjects would be infection given extra manipulation prior to intravitreal injection. These risks will be minimized by using sterile culture techniques. All cultures will be followed by application of povidone iodine to comply with current recommendations to sterilize conjunctiva prior to intravitreal injection. It is also possible that patients will experience increased discomfort due to the conjunctival cultures. Per the protocol, cultures will follow topical anesthetic application.

Data collection:

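### The written arms do not isolate an extra proparacaine drop given after povidone-iodine: one arm gets one more anesthetic and one fewer conjunctival povidone-iodine application

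*Combined protocol and SAP*

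**What the plan says.** The Introductory Statement makes patient experience the first aim, compared according to whether proparacaine is given once povidone-iodine (PI) has been applied. It adds an antisepsis aim: the added drop should do no harm. The end of section A.6 (Significance) describes the proposal the same way, as the usual drop before PI and one more afterwards. The Indication reads: "To compare the effects of proparacaine before and after povidone iodine application on patient experience".

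The General approach/Treatment plan then sets out the steps. Every patient first receives proparacaine. Next: "A conjunctival culture will then be obtained followed by the application of povidone-iodine to the eyelashes and eyelid margins". Lid retraction and randomization come after that:

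- First-described arm: "At this point, half of the patients will be randomized to receive 5% povidone-iodine drop to the conjunctival surface". Its second culture is taken at that stage, PI goes onto the conjunctiva a second time, and the needle comes last.
- Other arm: "The other half of patients will undergo application of another drop of topical anesthetic followed by conjunctival culture". Only once that swab is taken does this arm get its single conjunctival PI application, and the needle comes last.

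The later Treatment plan section repeats this sequence. The Human subjects section gives a reason for PI after each culture: "All cultures will be followed by application of povidone iodine to comply with current recommendations to sterilize conjunctiva prior to intravitreal injection". Figure 1 is cited for the sequence, with a note that "the circles highlight deviations from the typical protocol", but the figure is not reproduced in the text available. Data collection, item c, says only that experience will be compared between groups and with existing data from the same survey.

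**The concern.** The aims describe arms that differ by one thing, an added drop after PI. The steps describe arms that differ by two: the second arm gains an anesthetic application and loses a conjunctival PI application. The gained application also comes before that arm's only conjunctival PI, not after it.

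The second difference bears on the endpoint by the plan's own account. Section A.6 cites a study in which 26% of patients named PI application as the most bothersome part of the process, against 10% for the injection. If the second arm reports a better experience, the anesthetic, the missing PI application, or both could be the reason. A reader of the aims would credit the proparacaine drop and its timing, which the comparison as written cannot support.

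The antisepsis aim is touched as well. It asks whether the extra drop interferes with PI, yet both cultures in the second-anesthetic arm are taken before that arm receives any conjunctival PI.

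**Working it through.** The plan gives no figure to reproduce here; the check is a count of steps.

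**Inputs.** The sequence comes from the General approach/Treatment plan and is the same in the later Treatment plan. The 60 patients come from Human subjects. The 30/30 split is an assumption based on the plan's half-and-half allocation.

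**Sequences.** Write A for anesthetic, C for culture, L for PI to lashes and lid margins, P for conjunctival PI and N for needle.

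- First-described arm: A, C, L, P, C, P, N
- Other arm: A, C, L, A, C, P, N

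**Counts.**

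| Item | First-described arm | Other arm | Difference (other minus first) |
|---|---|---|---|
| A | 1 | 2 | +1 |
| P | 2 | 1 | −1 |
| L | 1 | 1 | 0 |
| C | 2 | 2 | 0 |
| A given after any P | 0 | 0 | 0 |
| A given after L | 0 | 1 | +1 |
| C taken after any P | 1 | 0 | −1 |
| C taken after both P and a second A | 0 | 0 | 0 |

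**In patients.** Anesthetic after conjunctival PI: 0 × 30 + 0 × 30 = 0 of 60. Anesthetic after lid and lash PI: 0 × 30 + 1 × 30 = 30 of 60. P is the last step before N in both arms.

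**What the experience comparison estimates.** Let *a* be the effect of the second anesthetic application and *p* the effect of having one conjunctival PI application fewer. Even in the simplest additive case, the between-arm difference is *a* + *p*. That is one equation in two unknowns, and no patient receives one change without the other, so neither a larger sample nor a different model separates them. As an illustration in assumed units, not taken from the documents, a net benefit of 10 fits *a* = 15 with *p* = −5, and equally *a* = −5 with *p* = 15.

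**What the second culture compares.** It follows conjunctival PI in one arm and precedes all conjunctival PI in the other. No culture in either arm follows both conjunctival PI and the extra drop.

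**The case against.** The strongest reply is that the aims speak of PI without specifying the conjunctival application. In the written sequence the second drop does follow PI to the lashes and lid margins, so in 30 of 60 patients it is literally after PI. On that reading the Indication's before-and-after wording can also describe the second arm. This stands as a possible reading, although section A.6 discusses PI in terms of its contact with the conjunctival surface. It rescues the word *after* but not the contrast, because the arms still differ by one conjunctival PI application.

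Second, the repeated PI has a documented reason: every culture is to be followed by PI. That explains the imbalance without removing it.

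Third, the sequence broadly fits other stated purposes. Section A.6 and Data collection, item b, want proparacaine's effect on cultures with and without PI. This is fair, and the conflict is therefore with the first aim and the proposal, not with every purpose in the plan.

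Fourth, Figure 1 is not visible and may show a different order, and the second copy of the treatment plan repeats the first, so it is not independent confirmation. A clause may simply have been dropped and then copied. This limits confidence about what was intended. It does not remove the need for action: if the figure differs, text and figure disagree; if it does not, text and aims disagree.

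Finally, the effect on results is unquantified. The 26% and 10% figures concern PI application as a whole and do not give the effect of one application more or less.

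**Conclusion.** The concern holds, and the plan should not stand as written. The arms differ by one more anesthetic and one fewer conjunctival PI application, and no patient receives an anesthetic after conjunctival PI. The procedure therefore does not isolate the contrast named in the first aim, on either reading of *after*, and the analysis described in Data collection, item c, cannot recover it.

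The randomized comparison of the two complete sequences remains valid; what is lost is attribution to the drop or its timing. The documents give neither the size nor the direction of either component's effect, so no bound on proparacaine's share can be stated. The survey items are not reproduced, so whether a step-level item could help is unknown.

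The conclusion rests on the written text, with the patient counts assuming a 30/30 split. Because Figure 1 could not be seen, confidence is medium.

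**What to change.** Reconcile the arm text, in both places where it appears, with the Introductory Statement, section A.6, the Indication and Figure 1. Which sequence is right is for the sponsor and investigator to settle; this review takes no position.

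- **If the written sequence stands:** restate the experience contrast as a second anesthetic application plus one conjunctival PI application, versus two conjunctival PI applications. Add a sentence to the analysis section saying that a difference will not be attributed to proparacaine alone or to giving it after PI. The cost is wording only, with no extra patients or assessments; the downside is a narrower claim.
- **If another sequence was intended:** the arm text needs a protocol amendment, and the culture comparison in section A.6 and Data collection, item b, has to be reviewed with it.

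In either case, check the antisepsis aim at the same time, stating which culture answers it and after which applications that culture is taken.

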Topical Proparacaine Eye Drops
to Improve the Experience of
Patients Undergoing
Intravitreal Injections

NCT# 02951351

September 07, 2016

STUDY NAME

INTRODUCTORY STATEMENT

The specific aims of this study are to compare patient experience with and without a proparacaine drop after povidone iodine. To ensure the extra drop does not interfere with antisepsis, conjunctival cultures will be obtained from patients undergoing intravitreal injection before and after the application of the extra eye drop.

A. Background information:

1. Intravitreal injections

Intravitreal injections are used to treat patients with many ocular conditions including: exudative age related macular degeneration, endophthalmitis, CMV retinitis, forms of choroidal neovascularization, e.g. diabetic retinopathy, and macular edema.

2. A feared complication, endophthalmitis

Endophthalmitis is a post-injection complication with great morbidity. A comprehensive review published in 2004 outlining the risk of endophthalmitis after intravitreous injection found a 0.2% prevalence per injection, which increased to 0.6% prevalence for injection with triamcinolone acetonide. All other injected medications had a risk of 0.1% per injection.[1] A 2011 study published in *Retina* reported that 1 out of every 4000 to 8000 injections of anti-VEGF medications results in endophthalmitis.[2] Finally, a study using a Medicare database found that of 41,000 injections, the rate of post-injection endophthalmitis was about 0.09% per injection.[3]

The specific bacteria that cause post-injection endophthalmitis have been reported in a study by McCannel as most commonly coagulase-negative *Staphylococcus* species in 65.4% of cases where a bacterium was identified. *Streptococcus* species were identified in 30.8% of endophthalmitis cases; most commonly viridans group streptococci (VGS), *S. salivarius*, and *S. mitis*. [4]

3. Preventative measures

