To prevent endophthalmitis, sterilization is attempted before injections using 5% povidone-iodine (PI), Betadine, which has been demonstrated to be as effective as topical antibiotics. [5] Povidone iodine's use prior to IVI is supported by a number of studies.[6, 7] Apt *et al.* demonstrated that one drop of povidone iodine administered preoperatively reduced bacterial colonies in conjunctival cultures by 91% versus 33% for control eyes.[8] Isenberg demonstrated that preoperative administration of povidone iodine was as effective as neomycin, polymyxin B, and gramicidin (Neosporin, Johnson & Johnson, New Brunswick, NJ) ophthalmic solution given three consecutive days prior to surgery in reducing conjunctival cultures.

STUDY NAME

Neosporin plus povidone iodine was more effective than either alone, leading to a 99.9% decreased colony count.[6] Overall, povidone iodine is nontoxic to the eye in the appropriate concentrations, has a broad antimicrobial spectrum (including bacteria, fungi, protozoa, and viruses), has a low propensity to select for bacterial resistance, is inexpensive, and is widely available.[9]

4. Antimicrobial properties of proparacaine

The antibacterial properties of proparacaine have been previously reported. A study on the effects of topical anesthetics on bacteria using a disk diffusion technique studied proparacaine and 0.5, 0.25, and 0.125% concentrations found that proparacaine inhibited the growth of *Staphylococcus aureus* at 1,250 µg/mL, and inhibited *Pseudomonas aeruginosa* growth at 2,500 µg/mL. [10] Proparacaine has also been demonstrated to have antimicrobial properties against *Staphylococcus epidermidis* and viridans group streptococci (VGS). It has been shown to reduce the number of culture-positive eyes, with 4 of 40 eyes being culture-positive after proparacaine, versus 12 of 36 eyes being culture-positive after receiving control solution, containing only preservative.[11] The mechanism by which proparacaine acts as an antimicrobial has been studied; it is thought to disrupt bacterial cell membranes causing permeability and lysis.[12, 13] Finally, benzalkonium chloride, the preservative component of proparacaine, has been demonstrated to have antimicrobial effects, with an *in vitro* study showing that benzalkonium chloride inhibits *S. aureus* growth.[14]

5. Background research (see attachment):

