Conjunctival cultures will be incorporated into the current intravitreal injection procedure

STUDY NAME

followed by Mayo Clinic.:

a. Conjunctival cultures

Bacterial cultures will be performed from conjunctival samples. Bacterial speciation will be performed on any bacteria that grows using the usual procedure to determine the bacterial species collected by the study.

b. Proparacaine Eye drops

Proparacaine 0.5% with preservative benzalkonium chloride 0.01% (Akorn) will be analyzed for its effect on bacterial growth *in vivo* with and without povidone iodine.

c. Data analysis and interpretation

Whether cultures are positive or negative will be compared between groups. Outcomes will also be measured by comparing the semiquantitative number of bacterial cultures (the microbiology lab will report cultures as 1+ through 4+) according to the Mayo Clinic Microbiology laboratory protocol. Patients who have positive cultures will have specific bacterial species determined which will also be analyzed. Demographic characteristics will be recorded including date of

STUDY NAME

birth and sex. Information surrounding the indication for injection will also be obtained as well as type of medication injected and number of previous injections. Finally, medication data will be included with specific focus on antibiotics—topical or systemic and eye drops.

In addition, patients will complete the previously detailed survey regarding their experience. Patient experience will be compared between groups and to existing data from this previously utilized survey described in PMID: 25901838.

Human subjects

Sixty patients (male and female) undergoing intravitreal injection who do not have active eye infections will be enrolled after undergoing informed consent.

Exclusion criteria: 1. Age less than 18. 2. Patients with active eye infections

The main risk encountered by human subjects would be infection given extra manipulation prior to intravitreal injection. These risks will be minimized by using sterile culture techniques. All cultures will be followed by application of povidone iodine to comply with current recommendations to sterilize conjunctiva prior to intravitreal injection. It is also possible that patients will experience increased discomfort due to the conjunctival cultures. Per the protocol, cultures will follow topical anesthetic application.

Treatment plan:

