After a procedural time out to verify patient, agent, and laterality, proparacaine will be applied to the ocular surface. A conjunctival culture will then be obtained followed by the application of povidone-iodine to the eyelashes and eyelid margins. The eyelids will then be retracted away from the intended injection site for the duration of the procedure. At this point, half of the patients will be randomized to receive 5% povidone-iodine drop to the conjunctival surface followed by conjunctival culture then re-application of 5% povidone-iodine drop to the conjunctival surface. A needle will then be inserted perpendicular to the sclera, 3.5-4.0 mm posterior to the limbus between the vertical and horizontal rectus muscles. The other half of patients will undergo application of another drop of topical anesthetic followed by conjunctival culture. After the culture, this group of patients will have 5% povidone iodine applied to the conjunctival surface. A needle will then be inserted perpendicular to the sclera, 3.5-4.0 mm posterior to the limbus between the vertical and horizontal rectus muscles.

STUDY NAME

Safety

The current protocol for intravitreal injections requires that patients be treated with povidone iodine immediately prior to intravitreal injection for antisepsis. The protocol for this study will not deviate from the standard protocol in that way. The safety of the study will be monitored by the PI. If more than 4 patients are noted post-procedurally to require additional return visits for conjunctival irritation or infection, the study will be discontinued.

3. Turan KE, **[name]**, Brodsky MC. Incipient white dot fovea syndrome in a child. *J AAPOS*. 2014 Aug;18(4):391-3. doi: 10.1016/j.jaapos.2014.02.007. Epub 2014 Jun 7.

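### Proparacaine's own effect on bacterial growth, and its interaction with povidone iodine, cannot be estimated, because every culture is taken after proparacaine

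*Combined protocol and SAP*

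**What the plan says.** **The stated analysis.** Data collection, item b (Proparacaine Eye drops), says that the product "will be analyzed for its effect on bacterial growth" in vivo, in the presence and in the absence of povidone iodine. Item c (Data analysis and interpretation) compares culture positivity between groups, and also uses a 1+ to 4+ grade. It specifies no within-patient analysis and no model.

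**The sequence.** General approach/Treatment plan and the later Treatment plan section agree:

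- All patients: "proparacaine will be applied to the ocular surface". Then: "A conjunctival culture will then be obtained followed by the application of povidone-iodine to the eyelashes and eyelid margins".
- One arm (call it A): "half of the patients will be randomized to receive 5% povidone-iodine drop to the conjunctival surface followed by conjunctival culture", then povidone iodine again.
- The other arm (B): "The other half of patients will undergo application of another drop of topical anesthetic followed by conjunctival culture". Then: "After the culture, this group of patients will have 5% povidone iodine applied to the conjunctival surface".

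The Human subjects sections confirm that cultures come after topical anesthetic.

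**The before-and-after wording.** The Introductory Statement says that "conjunctival cultures will be obtained from patients undergoing intravitreal injection before and after the application of the extra eye drop".

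**Background evidence.** Background, item 4, cites a study with "4 of 40 eyes being culture-positive after proparacaine, versus 12 of 36 eyes being culture-positive after receiving control solution". It adds that the control solution contained the preservative only.

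**The concern.** To estimate what proparacaine does to bacterial growth, some cultures must be free of it. To estimate that effect both with and without povidone iodine, proparacaine-free cultures are needed under each condition. The sequence supplies none.

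The matter bears on how the results may be used. Background, item 6 (Significance), suggests that proparacaine's antimicrobial action may make it acceptable after povidone iodine. Suppose growth falls from the first to the second culture in arm B. Item b, together with the before-and-after wording, invites the reader to credit that fall to proparacaine. Nothing in the plan warns against this, and the data could not support it.

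**Working it through.** The plan gives no power, effect size or sample-size calculation, so there is no figure to reproduce. The question is which effects the cultures can separate.

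**Step 1. Write each culture as a sum of effects.** Let μ be the level with nothing applied, P the effect of any proparacaine, P2 the increment of a second drop, L lid povidone iodine, C conjunctival povidone iodine, and T elapsed time plus the first swab.

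| Culture | Applied beforehand | Expected level |
|---|---|---|
| First, both arms | proparacaine | μ + P |
| Second, arm A | plus lid and conjunctival povidone iodine | μ + P + L + C + T |
| Second, arm B | plus lid povidone iodine and a second drop | μ + P + P2 + L + T |

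There are three distinct conditions and six parameters. The design matrix has rank 3.

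**Step 2. See what can be estimated.**

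- P appears only in the sum μ + P, so proparacaine versus none cannot be estimated.
- Second culture, B minus A: (μ + P + P2 + L + T) − (μ + P + L + C + T) = P2 − C. L and T cancel. This is a second anesthetic drop versus a conjunctival povidone iodine drop.
- Change within arm B: P2 + L + T.
- Change within arm A: C + L + T.

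**Step 3. Relax the assumptions.** Set L = T = 0. P2 and C can then be estimated from the within-arm changes. P still cannot. Nor can an interaction of proparacaine with povidone iodine: there is no proparacaine-free culture, and no culture follows both a second drop and conjunctival povidone iodine.

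**Step 4. Try the other order.** The Introductory Statement and the end of Background, item 6, describe the extra drop as following povidone iodine. In the treatment plan it follows the lid application but precedes any conjunctival povidone iodine in arm B. Figure 1 is not available here. If arm B had conjunctival povidone iodine before the extra drop and the second culture, its level would be μ + P + P2 + L + C + T, and B minus A would equal P2, the increment of the drop on top of povidone iodine. P would remain tied to μ, so proparacaine's effect without povidone iodine would still be out of reach.

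**Step 5. Illustrate the number of positive first cultures.** Assume that the cited post-proparacaine rate applies here.

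- 4/40 = 10%; exact 95% interval 2.8% to 23.7%.
- Among 60 first cultures: 60 × 0.10 = 6, with a range from 60 × 0.028 = 1.7 to 60 × 0.237 = 14.2, so about 2 to 14.
- In arm B (30 patients): 30 × 0.10 = 3, with a range of about 1 (30 × 0.028 = 0.8) to 7 (30 × 0.237 = 7.1).
- If all 3 turned negative and none turned positive, the exact two-sided McNemar p is 2 × 0.5³ = 0.25. With 7 it would be 2 × 0.5⁷ = 0.016.

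At 10%, then, the within-arm change in positivity is uninformative. Near the top of the range it could look convincing while still being P2 + L + T.

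**The case against.** **Item b is a loose line, not an estimand.** Background, item 6, speaks of comparing cultures after proparacaine alone and after proparacaine with povidone iodine. The second cultures partly do that, and item c's comparison is between groups. This is a fair reading of intent and supports treating the point as one of wording. But such a comparison estimates what povidone iodine adds, set against a second drop. It is not an effect of proparacaine.

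**Proparacaine's antimicrobial efficacy is not a specific aim.** This stands. The aims are patient experience and assurance that the extra drop does not impair antisepsis. It limits the weight of the point; item b still promises an analysis that the design cannot deliver.

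Three stronger readings are tempting and are not supported:

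- *Lid povidone iodine spoils the culture comparison.* Both arms receive it before the second culture, so it does not bias the randomised contrast. It confounds only the change within an arm.
- *The plan intends to infer proparacaine's effect from the within-arm fall.* The Introductory Statement mentions cultures before and after the drop, but item c specifies no such analysis. The risk is a misreading that the plan leaves open.
- *Proparacaine's effect is used up before the first culture, giving about 6 positives in place of about 20.* The 20 would be 60 × 12/36. That comparator received preservative solution, so 33% is not an untreated rate; its exact 95% interval is 18.6% to 51.0%. The rates come from another study, and the protocol gives no interval from drop to swab.

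**Conclusion.** The point holds. As written, item b describes an effect that the design cannot estimate: every culture follows proparacaine and no arm omits it. This follows from the sequence and depends on no assumed rate. A larger sample would not help, and neither order of the extra drop changes it.

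Two limits apply. First, the randomised second-culture comparison is valid for what it compares, which as written is a second anesthetic drop versus a conjunctival povidone iodine drop. Its exact meaning cannot be settled until the sections on the order of the drops agree. Second, the estimate of 2 to 14 positive first cultures is an illustration that assumes the cited study's rate carries over.

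The patient-experience comparison is a separate question and is not touched by this point.

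**What to change.** 1. Reconcile the Introductory Statement and the end of Background, item 6, with the two treatment-plan sections on whether the extra drop comes before or after conjunctival povidone iodine. This comes first because it determines which contrast the second cultures estimate.
2. Restate Data collection, item b, as the between-arm comparison of second cultures, adjusted for the first-culture result, and name the contrast. On the sequence as written, that is a second anesthetic drop versus a conjunctival povidone iodine drop.
3. Label changes from the first to the second culture within an arm as descriptive, and say that they also reflect lid povidone iodine, elapsed time and the first swab.
4. State that the trial will draw no conclusion on proparacaine's own antimicrobial effect or on its interaction with povidone iodine.

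**Cost.** Items 2 to 4 need only wording and an adjustment that uses a culture already being collected; they add no patients, swabs or procedures. The sponsor gives up a claim that the data could not have supported. Item 1 needs a decision by the sponsor and the investigator, on which this review takes no position.
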